completion of all the drinks they will have a 15-minute absorption period. Participants will consume these beverages with a trained research staff member (graduate or undergraduate research assistant) to add a social aspect. This individual will be introduced as a staff member not a confederate and will not consume any alcoholic beverages⁶⁷. After the drinking portion has ended the participant will use the app again, be given a glass of water, and a BrAC will be taken. After 30 minutes, another BrAC will be taken, followed by self-reports. Drink administration will be conducted per NIAAA guidelines⁷⁵ by 3 staff (supervisor, bartender, assistant). The individual drinking session can take place between 11am-7pm and participants should expect to remain on site for at least 2 hours after the drinking portion has ended and will be released when BrAC≤.02%. At that, time transportation will be arranged to take participants to their home address only. Payment for this session will be \$10 an hour and payment will be distributed at the follow-up appointment.

| Table 1. Summary procedures involved in individual alcohol drinking sessions in the proposed study | |
|--|--|
| Time | Procedures |
| +0 | Arrival. Breath alcohol (BrAC) reading, urine testing, snack, US-THRIVE, app assignment, app information, & instructions, use app. |
| +60 | Alcohol dosing period: dose targeting BAC=.06, divided into three parts, 10 minutes to drink each part of dose |
| +90 | 15 minute absorption period, participant drinks small glass of water to rinse alcohol from mouth |
| +105 | BrAC, use app, self-report of perceived impairment & other measures, then BrAC |
| +135 | BrAC, use app, self-report of perceived impairment & other measures. |
| +165 | BrAC. Dismissal once BrAC ≤ .02% |

Group Alcohol Drinking Session:

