| 5:45 | Breath alcohol (BrAC) reading, use app, self-report of perceived impairment & other measures, then BrAC |
| 6:15 | 1-hour free-drinking period when participants can self-administer more vodka mixed drinks to max BAC=.12% |
| 7:15 | Participant drinks small glass of water to rinse alcohol from mouth, then BrAC |
| 7:45 | BrAC, use app, all participants will get feedback on performance, self-reported impairment/other measures |
| 8pm | Food provided, participants' phones returned and staff extracts data from study phones. |
| 10pm | Usability ratings of assigned app, 4-week field period explained, experimental feedback app provided to all |
| 11pm | Earliest possible dismissal once BrAC \leq .02% |

App condition: The control version is a smartphone-compatible CGNG. Each trial has this order: fixation cross (250ms); blank (250ms), vertical or horizontal cue (white rectangle) for 1 of 6 stimulus onset asynchronies (100, 200, 300, 400, 500, 750ms); go or no-go target (green or blue rectangle, respectively) until participant responds or 500ms; inter-trial interval (250ms). Participants are told to respond fast to green, not to blue. Cues signal a target at 70% probability (horizontal: go, vertical: no-go). Activation and inhibitory tendencies develop cue-dependence^{70, 71}. Go cues speed RT to go targets, which must be overcome for no-go targets.

Inhibition errors are more common after go cues. The app is the same as a computer version except it fits a smartphone (Fig. 2b) with instructions to press the screen directly rather than a keyboard and includes 75, not 250 trials.

The standard version is the same as the control version with the exception that information about performance (correct or incorrect) is displayed along with RT in ms for a correct response during each inter-trial interval.

[figure not shown]

Figure 3. *Example* partial Decision Tree for CGNG Experimental Feedback App use

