Normal probability plots will be reviewed to assess normality and need for transformations. Paired samples *t*-tests will be used to confirm an effect of initial dose on CGNG inhibition errors but not RT. Our analytic strategy will resemble 3 past studies. The main method will be multiple regression with study condition and sex as predictors. Baseline variables that differ significantly by condition will be covaried.

Outcome 1a will be BAC during self-administration. Because we will not interrupt alcohol self-administration with BrAC readings, we will calculate peak estimated BAC (eBAC) based on number of alcoholic drinks, time elapsed, weight and sex. eBAC was sensitive to differences in consumption between study conditions in a prior study conducted by [name]. Results will be BrAC-confirmed after the 1-hr free-drinking period. Though not the main focus, we will test 2-way interactions of study condition by RT and inhibition errors post-alcohol to see if more inhibition failures under alcohol predict self-administration. Regressions will be confirmed using multilevel models (MLM) in Mplus with random effect of group (people completing a drinking session together) and other predictors as fixed effects. Since participants will be randomized to different apps, we do not expect strong intra-class correlations, which should result in similar findings in regression and MLMs. In our in-progress study, no group level effects have emerged. A similar strategy will be used for 1b (alcoholic drinks self-administered).

Primary Aim 2 will entail comparisons of alcoholic drinks consumed per occasion between the 2 weeks participants will use vs. not use the app in the 4-week field period post-drinking session. We will retain study condition as a predictor (effects of lab-assigned condition are not hypothesized here) and a random group effect while adding app use vs. non-use period as a within-subjects effect in MLM. ANOVA will compare usability and acceptability ratings at the end of the drinking session and 4-week field period across app conditions. For mediation (Secondary Aim), we will test for indirect effects of app condition on self-administration via perceived impairment using MacKinnon’s products of coefficients approach with bootstrapped confidence intervals (CIs). This approach accounts for non-normality of the product of

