coefficients in calculating indirect effects of IV on DV, operating through a mediator. When the CI does not include 0, an indirect effect is significant at the specified alpha level.

For Exploratory Aim 1, we will test between-subjects study condition during the lab sessions, amount of alcohol self-administered (operationalized as estimated peak BAC and number of drinks self-administered in separate models) in the alcohol drinking session and during the field period in the intervention and non-intervention periods as predictors of self-reported alcohol consumption (e.g., drinks per drinking day) and alcohol-related problems self-reported at 6- and 12-months post-session on the web-based surveys using MLM. Baseline reports of each alcohol-related outcome and participant sex will be entered as covariates. The web-based surveys at baseline, 6- and 12-months post also include measures of several potential covariates that may be entered into these models should they differ significantly across study conditions.

For Exploratory Aim 2, we will use separate MLMs to test BACTrack Skyn readings during each alcohol administration session as predictors of successive breath alcohol readings taken following alcohol administration/self-administration periods in the alcohol drinking sessions and to predict number of drinks self-administered during the group drinking session. Sex and participant weight will be entered into these models as covariates as well.

For Exploratory Aim 3, we will use MLM to predict expected involvement scores on the CARE measure post-alcohol administration based on performance on the app-based cued go/no-go task following the .06% fixed dose as the predictor variable. Baseline expected involvement scores and scores on the other CARE subscales will be held constant in these models. Since the .06% dose will be administered at each session along with cued go/no-go task performance and the CARE, these measures will be entered into the same models as repeated measures. Participant sex and study condition will also be entered as covariates in these models

Sample, power & effect size

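### Exploratory Aim 2: with no time term named, the Skyn coefficient for breath alcohol is confounded with time since dosing if repeated readings are paired

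*Combined protocol and SAP*

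**What the plan says.** The Exploratory Aim 2 paragraph under Data analyses plans "separate MLMs to test BACTrack Skyn readings during each alcohol administration session as predictors of successive breath alcohol readings". It adds a second outcome, using Skyn "to predict number of drinks self-administered during the group drinking session". On covariates it says "Sex and participant weight will be entered into these models as covariates as well". It does not mention reading occasion, time since dosing or random effects for this aim. It also does not say how Skyn readings are summarised or matched to breath readings.

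Other parts of the same section are more explicit about structure:
- Primary Aim 2 carries app-use period as a within-subject effect.
- Exploratory Aim 3 pools its two sessions: "these measures will be entered into the same models as repeated measures".
- The estimated-BAC calculation for Outcome 1a uses elapsed time alongside drinks, weight and sex.

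The schedule is common to all participants. Table 1 (individual session) gives, at +60, "Alcohol dosing period: dose targeting BAC=.06, divided into three parts, 10 minutes to drink each part of dose". Absorption follows from +90 to +105. Breath readings come twice in the +105 block, then at +135 and +165. Table 2 (group session) repeats the fixed dose at 5pm, with two breath readings in the 5:45 block. From 6:15 there is a "1-hour free-drinking period when participants can self-administer more vodka mixed drinks to max BAC=.12" percent, with readings at 7:15 and 7:45 and release later, once breath alcohol is .02% or lower.

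Wearing the Skyn is optional and the number of wearers is not given. Power is stated for the Primary and Secondary Aims only.

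**The concern.** A shared dose and a shared reading schedule give breath alcohol a time course that is partly common to all participants. A wrist sensor responding to the same dose also has a common time course, possibly delayed. A model that regresses one repeated series on the other without time picks up the association between the two average curves, whatever the sensor says about an individual.

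Two readings of a significant coefficient then cannot be told apart: that the sensor carries information about this person's level, or that time has passed since the dose. The sign is not secure either. A sensor that follows alcohol late can still be rising while breath alcohol falls. More participants on the same schedule do not help, because the confounding stays and the standard error shrinks.

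**Working it through.** The plan gives no figure for this aim, so there is none to reproduce. All variances, lags and numbers of wearers below are assumptions.

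**1. The model under one reading of the text.** Suppose Skyn and breath readings are paired at each occasion, with a participant random intercept (itself an assumption):

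BrAC(i,t) = b0 + b1·Skyn(i,t) + b2·sex(i) + b3·weight(i) + u(i) + e(i,t)

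If the average curves of BrAC and Skyn are correlated over the reading times, b1 is non-zero even when the two are independent at any given time.

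**2. The sign, by hand (individual session).** Assume a linear rise to .060 between +60 and +105, then a fall of .015 per hour. The second reading of the +105 block is placed at +130. The sensor is a noiseless copy of the curve, 60 minutes late.

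| Time | BrAC (units of .01) | Sensor (units of .01) |
|---|---|---|
| +105 | 6.000 | 0 |
| +130 | 6 − (25/60)(1.5) = 5.375 | (10/45)(6) = 1.333 |
| +135 | 6 − (30/60)(1.5) = 5.250 | (15/45)(6) = 2.000 |
| +165 | 6 − (60/60)(1.5) = 4.500 | 6.000 |

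The means are 5.281 and 2.333. The sum of cross-products is −1.677 − 0.094 + 0.010 − 2.865 = −4.625. The sensor sum of squares is 5.444 + 1.000 + 0.111 + 13.444 = 20.0. The slope of the average curves is −4.625/20.0 = −0.23. With no lag the two curves coincide and the slope is +1 before noise. Lag alone reverses the sign.

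**3. Simulation A: a sensor with no person-specific information.** The sensor is the average curve times a random gain, plus noise. Assumptions: the curve above, BrAC noise SD .004, Skyn noise SD .008, extra self-administered BAC with mean .03 and SD .015, and two late group readings at 300 and 360 minutes. There were 100 replicates per cell and sessions were fitted separately. Entries are the share with Skyn p<.05, at n = 40 / 99.

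| Readings | Lag (min) | No time term | With occasion | Mean slope, no time term |
|---|---|---|---|---|
| Individual, 4 | 0 | 98% / 100% | 5% / 5% | +0.26 / +0.25 |
| Individual, 4 | 30 | 100% / 100% | 6% / 1% | −0.18 / −0.17 |
| Individual, 4 | 60 | 100% / 100% | 8% / 5% | −0.20 / −0.19 |
| Group, first 4 | 0 | 73% / 94% | 8% / 6% | +0.20 / +0.17 |
| Group, first 4 | 30 | 9% / 21% | 11% / 7% | +0.02 / +0.03 |
| Group, first 4 | 60 | 78% / 97% | 23% / 16% | +0.09 / +0.09 |
| Group, 6 | 0 | 100% / 100% | 8% / 3% | +0.68 / +0.67 |
| Group, 6 | 30 | 99% / 100% | 9% / 11% | +0.22 / +0.21 |
| Group, 6 | 60 | 25% / 58% | 22% / 17% | −0.06 / −0.06 |

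With occasion added, the mean slope was within 0.02 of zero in every row. The simulation error at a true 5% is √(.05×.95/100) = 2.2 points, so the 16-23% cells are a real excess.

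**4. Simulation B: different assumptions.** Skyn is independent of BrAC given time. Skyn person and reading SDs are 1 unit each. BrAC person SD is .010, with reading SD .006 (individual) or .010 (group). There were 600 replicates per cell, with an error of √(.05×.95/600) = 0.9 points at 5%. It used three individual-session readings, one fewer than Table 1 lists. Entries are false positives without a time term.

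| Session | Shared change | n=30 | n=50 | n=99 |
|---|---|---|---|---|
| Individual | BrAC −.010/h, Skyn 0.5/h | 20% | 26% | 46% |
| Individual | BrAC −.010/h, Skyn 1/h | 54% | 75% | 97% |
| Group, 4 readings | BrAC +.010, Skyn 0.5 | 18% | 27% | 39% |
| Group, 4 readings | BrAC +.010, Skyn 1 | 48% | 68% | 93% |

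The smallest Skyn shift tried (0.25 unit) gave 6-25%, and the full grid ran from 6% to over 99%. Adding occasion gave about 3-8%.

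**5. A further check, individual session.** With four readings, assumed variances and 60 replicates per cell, an uninformative sensor was significant in 100% of runs without time. An informative but lagging sensor got a negative slope. Adding occasion gave about 2-13% false positives and restored the positive sign.

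**The case against.** The strongest objection is that the plan contains no model equation. The paired form in step 1 is one reading of a short description. If Skyn were reduced to one value per person per session, such as a peak, and reading times were balanced, a shared clock trend could not load on its coefficient. This stands, so the point is conditional on pairing. The plan's reference to successive readings in multilevel models makes pairing a natural reading.

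Four stronger inferences are tempting, and the documents do not support them.
- **A missing session term is a defect.** The text speaks of separate models and of readings in each session, which may mean one model per session. Exploratory Aim 3, by contrast, says outright that its sessions are pooled.
- **The whole rise and fall is common to everyone.** Individual-session readings after dosing start once absorption is over, so they mainly show decline. In the group session, intake after 6:15 is each person's choice and may be nil, which is what a sensor ought to track. Late readings depend on when a person reaches .02%.
- **The clock effect always favours the sensor.** The slope can be positive, negative or near zero.
- **Adding occasion fully restores the error rate.** Simulation A shows otherwise in the group session.

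It can also be said that following alcohol through a session is part of what such a sensor is for, and that conditioning on occasion asks a narrower question. That is a reason to report the unadjusted tracking as description. It does not rescue a claim of prediction, because elapsed time is known without the device.

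**Conclusion.** The concern holds in a limited form. For the Exploratory Aim 2 breath-alcohol models no time or occasion term is named. If repeated Skyn readings are paired with successive breath readings, the Skyn coefficient is confounded with time since dosing. The shared course is mainly a decline in the individual session, and partly shared, partly self-chosen in the group session.

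The size cannot be fixed from the documents. Across the two main simulations an uninformative sensor tested significant in 6% to 100% of runs without time. With occasion added the rate was 1-8% in the individual session and 3-23% in the group session. These figures rest on the assumed variances, curve, sensor lag and number of wearers. That an informative but late sensor can get a negative slope follows from the lag arithmetic and was seen in the further check.

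A reader might infer that Exploratory Aim 2 as a whole, or the trial's main results, are compromised. They are not. Drinks self-administered is one value per person with no repeated time course, and no primary or secondary conclusion uses these models. The change is worth making before analysis because it gives a better model at almost no cost.

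**What to change.** In the Exploratory Aim 2 breath-alcohol models:
- State how Skyn readings are summarised and paired with, or lagged to, breath readings, and whether the sessions are pooled.
- Add scheduled reading occasion as a categorical fixed effect, or flexible time since dosing where late readings do not fall at common times. Add session only if both sessions share a model.
- Include a participant random intercept, with random slopes or residual autocorrelation as a check, since the intercept alone may leave some excess error.
- Base the claim that Skyn predicts breath alcohol on its gain over a model with occasion, sex and weight. Report the unadjusted within-session tracking as descriptive.

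The cost is a few sentences of plan text and a few degrees of freedom. Scheduled occasion is already available from Tables 1 and 2. Finer pairing needs recorded clock times, which the documents do not explicitly promise. The Skyn association will probably look weaker than the unadjusted one.

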Participants will be otherwise healthy men and women between the ages of 21-25 who frequently engage in heavy alcohol use. This study will test an app based on the cued go/no-go (CGNG) task giving in-the-moment feedback on impaired inhibitory control as an adjunct to an existing, web-based intervention (US-THRIVE) targeting general drinking patterns using M.I. principles. This new app will give in-the-moment feedback comparing pre- and post-drinking RT and errors, referring to evidence that poor CGNG response relates to poor simulated driving and willingness to engage in risky behavior. After feedback, the app will offer advice on slowing drinking and other options to avoid harm (e.g., a taxi). The experimental app—derived from a larger app (Robert Wood Johnson Foundation grant #73293, PIs: [name]/[name])—will be compared to standard (trial-by-trial RT and error information only) and control versions (no information) without feedback. After US-THRIVE, heavy drinking young adults will be randomized to 1 of the 3 apps. After initial use of their randomized app, they will then be dosed to .06% BAC during an individual session in a naturalistic lab, followed by app use. After this initial session, on a separate day, participants will attend a group session including 2 other participants. During this group session; they will again be dosed to .06% BAC, followed by app use, then 1-hr when they can self-administer alcohol up to .12%. There will be at least one day between the individual and group sessions and the goal will be for the individual and group session to occur within 7 days of each other. For 4 weeks post-session, all participants will use the experimental app for 2 weeks in real drinking occasions and not use it the other 2 weeks. Participants completing both the laboratory alcohol administration and field testing components of the study can earn up to \$450 during the course of study participation. Participants may also be invited to complete only field use of the app due to the COVID-19 pandemic or because they cannot physically come to the study location on campus. Among these participants, some will be invited to complete the four-week field use period as described above (i.e., 4 weeks total, 2 weeks with app access, 2 weeks with not and a brief daily questionnaire each day for the 4 weeks). Maximum possible payment for those chosen to complete only the field use period will be \$310. A small subset (up to n= 12 participants) will be selected to complete an ecological momentary assessment based field period of 10 days in which participants will be prompted multiple times per day to either use the app or to complete a brief questionnaire. Maximum payment for those completing the ecological momentary assessment will be \$200. We anticipate enrolling 208 participants, of whom 109 will be eligible with a target of 99 individuals completing the study.

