Preliminary steps: Participants who are invited back for a group alcohol drinking session will be asked not to eat for 3 hours pre-arrival. Alcohol drinking will occur either in a bar lab or other room located at Yon Hall North in Ben Hill Griffin Stadium at the University of Florida campus. At around 3:45pm, participants will be brought to the bar or simulated laboratory for the session via study-provided transportation: either a professional service such as taxi or Uber or a UF-owned automobile driven by a UF employee (Table 2). However, if a participant lives within a 0.5 mile radius of the research facility they may walk to the facility rather than being driven. At the end of the session, these participants may be walked home by study staff. Upon arrival at 4pm, BrAC (must=.00%) and urine tests will be repeated (Table 2). Participants registering a BAC > 0.00% or with a positive urine test that leads to exclusion will be dismissed immediately and provided transportation directly home by the study. At this appointment, participants will receive an abbreviated version of the instructions on how to use the app and its value (see below). Participants will also complete baseline self-reports and the cued go/no-go task on the app. Before the alcohol administration, participants may be asked to wear the BACTrack Skyn. Each session will be scheduled with 3 people each assigned to a different app, but if 1 cannot participate, the session may still occur. While it is our preference that this appointment occur at 4pm just before the rest of the drinking session activities, if a participant's schedule does not permit it, the 4pm activities may also be scheduled earlier in the day on the day of the session or the day before. In the case of an appointment the day before, the urine drug and pregnancy test will still occur on the day of the session. Payment for this appointment will be \$20 via cash card and will be transmitted on the day of the appointment.

Instructions: The day of the group session participants will be given a brief review of the instructions that were given to them at their individual drinking sessions. Participants will be asked to not share their results on the app with the other participants. Study staff will explain to participants that to incentivize fast, accurate performance (Fig. 2a), they will get \$.10 each

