Eligibility Checklist: This checklist is used by study staff to determine participant eligibility based on measures taken during the screening appointment to make certain that active evaluations of eligibility and ineligibility are made.

Screening and at Alcohol Administration Sessions:

Breath alcohol concentration: Breath alcohol concentration will be assessed using a hand-held Intoxilyzer breathalyzer unit at the in-person screening; at the preliminary appointment earlier on the day of the alcohol drinking session; at the outset of the alcohol drinking session and then at several points during the sessions.

Alcohol purchase task: This is a simulation measure to assess self-reported alcohol consumption and expenditure were alcohol to cost varying amounts of money. The measure generates a number of variables pertaining to reinforcement from alcohol, including intensity of demand. The purchase task will be administered twice during the in-person screening appointment. One version will assess how many drinks a participant would consume right now at varying amounts of money and a modified version will assess how many drinks a participant would consume on a hypothetical weekend evening. At the alcohol drinking session, the “right now” version of the measure will be administered multiple times at both at baseline and after the drinking period. This will allow a comparison of the amounts of hypothetical money participants are willing to spend on alcohol, a priori, upon arrival at the bar or simulated lab and after consumption of alcohol.

Risk Taking Behavior: The *Cognitive Appraisal of Risk Events* (CARE) and its revised version (CARE-R; Katz, Fromme, & D'Amico, 2000) assess recent negative consequences and expectations that these consequences will occur again in the near future. Of the measure's 4 subscales, we will administer at in-person screen a version of the past frequency subscale that combines the original with the revised version in order to obtain baseline data. Participants will be asked to report how many times in the past 3 months each has occurred. Then after fixed dose in the individual session, we will administer the expected involvement subscale. Items are rated a 7-point Likert scale ranging from “not at all likely” to “extremely likely”.

Alcohol Administration Sessions:

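### Exploratory Aim 3 adjusts for a baseline CARE expected-involvement score that has no named collection point, and the sections differ on which sessions include the CARE

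*Combined protocol and SAP*

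**What the plan says.** The combined protocol and SAP deals with this aim in three places.

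- **Data analyses, Exploratory Aim 3.** The outcome is the post-alcohol CARE expected-involvement score, and the predictor is performance on the app-based go/no-go task after the fixed dose. On covariates: "Baseline expected involvement scores and scores on the other CARE subscales will be held constant in these models". Sex and study condition are added. On structure, the sessions are treated as repeated measurements within one model: "Since the .06% dose will be administered at each session along with cued go/no-go task performance and the CARE, these measures will be entered".
- **5. Specific Aims, Exploratory Aim 3.** The aim is framed around the fixed dose in each of the drinking sessions.
- **Assessments, Risk Taking Behavior**, under the heading "Screening and at Alcohol Administration Sessions". This is the only place that describes how the CARE is administered. It says that the measure has four subscales. At in-person screening, participants complete a version of the "past frequency subscale that combines the original with the revised version in order to obtain baseline data". It continues: "Then after fixed dose in the individual session, we will administer the expected involvement subscale".

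Other sections mention self-reports without naming the CARE. For the group session, the preliminary steps say: "Participants will also complete baseline self-reports and the cued go/no-go task on the app". The measures listed for the start of a session are craving and mood. The arrival row of Table 1 (individual session) reads in part "urine testing, snack, US-THRIVE, app assignment, app information" and mentions no self-report.

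**The concern.** The analysis text requires the pre-alcohol value of its own outcome as a covariate. The measurement text names a different subscale as the baseline and mentions expected involvement only after alcohol. The two sections do not fit together.

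At stake is what the model can separate. Some people expect to take risks whether sober or not. A pre-alcohol expected-involvement score would let the model distinguish that habitual level from the level reported after the dose. Past frequency adjusts for part of it, but it counts past events over three months and is not the same scale taken sober. Unlike most analysis choices, this one cannot be repaired once participants have been dosed without the score.

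A second, smaller issue is the repeated-measures structure. It needs the CARE at both sessions, and the measurement text names one.

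**Working it through.** No formula or stated figure is involved. The check compares what the model needs with what the schedule names.

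**1. Pre-alcohol expected involvement.** Needed by Data analyses: 1 score. Named in Assessments: 0. The CARE baseline named there is past frequency.

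**2. Baseline CARE terms overall.** The measure has 4 subscales. Assessments names 2 of them at any time: past frequency at screening, and expected involvement after the dose. The subscales with no named collection point at all are 4 − 2 = 2. For the covariates there are two readings:

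- If the other subscales means all three remaining ones, the model needs 1 + 3 = 4 baseline terms. One (past frequency) has a collection point, so 4 − 1 = 3 do not.
- If it means only those that the study gives, the model needs 1 + 1 = 2 terms, and 2 − 1 = 1 has no collection point.

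Baseline expected involvement is unnamed on either reading.

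**3. Could a generic slot supply it?** The baseline self-reports in the group session do not name the CARE. They also come too late to serve as a pre-alcohol baseline for the individual session, because the Overview says: "There will be at least one day between the individual and group sessions". By then the participant has already been dosed once and has used the assigned app. The description of in-person screening and the web survey tied to it do not name expected involvement either.

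**4. Sessions.**

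| Section | Sessions with a post-dose score |
|---|---|
| Specific Aims, Exploratory Aim 3 | each session (2) |
| Data analyses, Exploratory Aim 3 | each session (2) |
| Assessments, Risk Taking Behavior | individual session named (1); group session neither named nor excluded |

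With one score per person there would be no between-session repeated measure to model.

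**5. Reach.** The section on sample, power and effect size addresses the primary and secondary aims, and these do not use the CARE. The documents give no correlation for this model, so the loss of precision or the residual confounding cannot be quantified.

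**The case against.** The strongest reply is that silence about timing does not show that the score goes uncollected. Data analyses presupposes the score, and Assessments does not say that expected involvement is given only after the dose. Table 1 is a summary and is visibly incomplete: its pre-dose row omits craving and mood, which another section places at the start of a session. It also omits the alcohol purchase task, which is given at baseline in the drinking session. An unlisted pre-dose CARE is therefore possible, and the silence of Table 1 is weak evidence against it. This stands, and it limits the point to the absence of a named collection point.

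It does not remove the point. Where the plan wants a measure both before and after drinking, it can say so. The purchase task entry does, directly above the CARE entry. The CARE entry instead picks a different subscale for baseline.

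On sessions, the reply is stronger. Specific Aims and Data analyses both affirm each session, the CARE entry sits under a heading that covers the sessions in the plural, and Table 2 has a post-dose slot for other measures. A reader might infer that the CARE is omitted from the group session. The documents do not support that inference; they are only inconsistent.

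A reader might also fault the plan for not saying which post-dose slot in Table 1 holds the CARE. For an exploratory questionnaire that is operational detail, and it is not part of this point.

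**Conclusion.** The point holds. The stated schedule does not supply a covariate that the stated model requires: one pre-alcohol expected-involvement score is needed and none is named. Two further subscales, which the covariate sentence may include, also have no named collection point. If staff follow the Assessments text, the baseline-adjusted model cannot be fitted as written.

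A reader might go further and conclude that the baseline score will not be collected. The documents do not show that; it would depend on staff following the Assessments entry to the letter. The difference over the group session is an inconsistency to reconcile and not proof of non-collection.

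Severity is minor. The effect is confined to Exploratory Aim 3. The primary and secondary aims and the justification of 99 participants are untouched.

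**What to change.** **Preferred.**

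- In Assessments, Risk Taking Behavior, add the expected-involvement subscale before any alcohol, for example at in-person screening next to past frequency.
- In the same entry, state that it is also given after the fixed dose in the group session, before the free-drinking hour.
- In Data analyses, Exploratory Aim 3, limit the other CARE covariates to subscales that are actually administered.

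The cost is a few questionnaire minutes at existing visits and edits to two sections.

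**If no pre-alcohol score can be added.** Remove baseline expected involvement from the covariates, adjust for past frequency, and state that the model does not adjust for the pre-alcohol value of the outcome. This is a wording change only. Its price is a weaker separation of habitual risk expectation from the level reported after alcohol. The session wording still needs to be reconciled.
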